# Intervention staff

Peer (Support) Workers, registered mental health nurses or other healthcare professionals or practitioners who are not trained for delivering the PEGASUS intervention for the purposes of this study.

### 7 TRIAL PROCEDURES

### 7.1 Recruitment

Recruitment will be conducted at four NHS mental health Trusts with their GP surgery/integrated care systems (ICS), community healthcare NHS Trust and community/voluntary sector partners.

In each of the four study sites we will recruit and train up to four peer workers and two mental health nurses (or other healthcare professionals/practitioners with appropriate training) to deliver the intervention.

We will recruit 10 (lower limit 8, upper limit 12) participants in each site (n=40 participants), using eligibility criteria as defined in section 6 above, to participate in a group clinic intervention running for four to six months. The intervention will comprise the full intervention model developed in the codesign process, except for any booster sessions after the end of the intervention. All participants will be invited to attend the intervention sessions. This study does not include a control arm.

## 7.1.1 Participant identification

Service user participants:

Electronic patient record of all people with SMI on the caseload of participating Trusts and SMI registers of participating GP surgeries/ICS will be screened by site clinical studies staff to identify possible presence of metabolic syndrome, as indicated by any one of:

- HbA1c > 37mmol/mol (5.5%), documented Impaired Glucose Tolerance or T2D;
- Blood Pressure > 130/85 or established hypertension;
- HDL level less than 0.9mmol/l (men), 1mmol/l (women);
- Fasting triglyceride level over 1.7mmol/l or prescribed with statin;
- BMI>25 in white participants or >23 in non-white people;
- 10-year QRISK3 score ≥ 10%

Potential participants will be identified by a) asking members of the direct care team in community mental health services and GP surgeries, and project leads in community (voluntary) sector organisations (including faith-based and cultural organisations) working with people with mental and physical health needs to give or send people who meet eligibility criteria project information (flyer plus participant information sheet which includes a summary top sheet as suggested by the LEAG) or b) placing flyers in community mental health service and community sector service delivery locations or c) local research staff (clinical studies team) will screen case registers and clinician caseloads in adherence with local Trust privacy notice permissions and consent to contact arrangements. Where potential participants express interest in being involved, they will be able to contact a member of the study team directly using contact information on flyers, or a member of their direct care team/ project team will be able to pass their contact details to the research team, as preferred.

In addition, we will contact people who attended health awareness/wellbeing events/workshops (and any similar events) run by sites outside the context of the study who agreed to be contacted about the research to assess their potential interest in participating in the trial.

All potential participants will be sent study information by email if available or by post (including Participant Information Sheet and any flyers or video-based information about the study that we might develop with the LEAG) and contacted by a member of the site's clinical studies team and invited to meet either in person or remotely by telephone or online videoconferencing application to discuss the study, have any questions answered and then invited to give informed consent to participate in the study (see 7.2). Interpreters will be identified from local providers used by study sites to support, either face-to-face or by telephone or videoconferencing application, to ensure that people with a first language other than English are able to participate in the research and intervention.

Peer worker and health professional participants:

Across the collaborating Trusts, we will work with the site PI and the local research and innovation team, Leads for Wellbeing Hub/Services, PW service, multi-disciplinary professional groups, to promote the study and invite interested PW and clinicians to join the study.

Interested staff members who have been trained to deliver the intervention will be provided with a participant information sheet about the focus group study and a meeting either in person or remotely via online videoconferencing or phone with a researcher to discuss the study and to clarify any outstanding queries. Informed consent will be obtained following at least a period of 24 hours.

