### 6 PARTICIPANT ELIGIBILITY CRITERIA

### 6.1 Inclusion criteria

### Service users

Participants will:

- Be aged 18 to 75 years
- Have capacity to consent to participate in research
- Currently on the caseload of mental health services in community settings or on GP/ ICS severe mental illness (SMI) list
- Current primary diagnosis of schizophrenia-spectrum disorders (ICD-10 diagnoses F20–29) or bipolar disorder (F31) or in Early Intervention for Psychosis Services (EIPS) with formal diagnosis of psychosis (ICD-10 diagnoses of F29) or an aforementioned diagnosis.
   If on psychotropic medication, on stable dose for 90 days (N.B. This refers specifically to either adding or changing to a new antipsychotic medication, but not applies to dosage adjustment of a pre-existing antipsychotic medication.)
  - o Enhanced CVD risk as indicated byany one of:Obesity defined as: waist circumference over 102cm in men (or >90cm in non-white men) or over 88cm in women (or >80cm in non-white women) or BMI≥25 kg/m² (or ≥23 kg/m² in non-white people)
  - Hypertension defined as: blood pressure over 130/85 mmHg or documented hypertension on medication
  - Dyslipidaemia defined as: fasting triglyceride level over 1.7mmol/l or total cholesterol
     ≥5.0 mmol/L or on medication for hyperlipidaemia (e.g. statin) or high-density lipoprotein (HDL) cholesterol level less than 0.9mmol/l (men)/1mmol/l (women)
  - Hyperglycaemia defined as: HbA1c > 37 mmol/mol (5.5%) or fasting plasma glucose level ≥5.6 mmol/l or documented Type-2 diabetes (T2D)
- If on treatment for T2D, hypertension or hyperlipidaemia, on stable dose medication for at least 90 days

For the purposes of the feasibility study, we will adopt a purposive sampling approach to identifying participants to ensure diversity in our sample in order that we obtain feedback on the intervention from racialised and other marginalised perspectives.

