# 7.1.2 Screening

# Service user participants

Following informed consent (see 7.2) obtained from identified service users as outlined above, participants will meet a research nurse in person who will go through the eligibility criteria screening (see section 6 for the Inclusion and Exclusion criteria). Demographic data including age, sex, ethnicity, will be collected. Cardio-metabolic risk data will be confirmed by a research nurse using Standard Operating Procedures to measure each indicator as defined above and as follows:

- waist circumference
- body mass index
- blood pressure
- full fasting lipid profile (including triglyceride level, high-density cholesterol, low-density cholesterol, and total cholesterol levels)
- HbA1c
- smoking status, tobacco, and betel nut or paan (or pan as it is also called) use
- alcohol consumption
- All variables collected from primary care records or by research nurse to calculate QRISK3 scores

The following data will be extracted from clinical notes, and further checked with participants:

- current mental health diagnosis
- current co-morbid physical health conditions
- current prescribed medication

Those that are eligible (as per 6.1) will go on to complete baseline data collection (See 7.6), and to be allocated to the intervention.

People identified with uncontrolled hypertension (i.e. either Systolic BP ≥200 mmHg or a diastolic BP >115 mmHg) or suspected of familial hypercholesterolaemia will be referred to their GP and will not continue in the feasibility study. People who are not eligible for the study because they do not fulfil criteria for metabolic syndrome or for other reasons will not continue in the feasibility study. They will be provided with evidence-based healthy lifestyle information by the research nurse and encouraged to make an appointment with their GP for their next annual physical health check.

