### 7.7 Trial assessments

At baseline only, we will collect participants' sociodemographic data and QRISK3. At baseline, 3-month and 6-month time points, participants will complete further psychometric, anthropometric measures, blood tests, and self-completed assessments, as follows:

- Psychiatric symptoms using the Modified Colorado Symptom index
- · Lifestyle behaviour, measured using:
  - o Diet Dietary Instrument for Nutrition Education (DINE)(49), adapted by IMPaCT(50)
  - o International Physical Activity Questionnaire Short Form (IPAQ-SF)(51)
  - Cigarette smoking, tobacco and betel nut or paan (also spelled as pan) use smoking/paan/pan use status and number smoked per day; number of paans chewed per week
  - Alcohol Alcohol consumption test (AUDIT-C)
- Health-related quality of life measured using the EQ5D-5L
- Depression measured using the PHQ9
- Self-efficacy measured using the Generalised Self Efficacy scale
- Social network measured using the Lubben Social Network Scale
- Therapeutic relationship measured using the STAR
- Progress towards achievement of personalised lifestyle goals, measured with the Goal-based outcome tool
- DIAMONDS Service Use Survey

Service user participants will also be asked to wear a wrist-worn accelerometer for one-week periods prior to the start and in months 3 and 6 of the intervention.

The following data on recruitment, questionnaire completion and intervention attendance will be collected during the intervention period:

- Number of participants screened
- Number with possible presence of metabolic syndrome and invited to participate in study
- Number confirmed as eligible after initial clinical assessment and invited to continue to take part in intervention
- Reason for declining participation where applicable
- Intervention session attendance
- Follow-up data completion rate (questionnaires and clinical data)
- Reason for dropout where applicable

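### The record-search list in section 7.1.1 does not match the risk criteria in section 6.1, which blurs the invited-to-eligible step of the recruitment funnel

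*Protocol*

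**What the plan says.** Section 7.1.1 says that records of people with SMI on Trust caseloads and GP registers "will be screened by site clinical studies staff to identify possible presence of metabolic syndrome, as indicated by any one of" six items. Among these are "documented Impaired Glucose Tolerance or T2D" (alongside HbA1c), "Blood Pressure > 130/85 or established hypertension", "BMI>25 in white participants or >23 in non-white people", and "10-year QRISK3 score ≥ 10" per cent. The remaining items are low HDL, and raised triglycerides or a statin prescription.

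Section 6.1 also admits on any one of a set of risk criteria, but the set is different. Its dyslipidaemia item, for example, reads "fasting triglyceride level over 1.7mmol/l or total cholesterol" at or above 5.0 mmol/L, and it accepts lipid medication in general, with a statin only as an example. Section 6.1 also lists waist circumference and fasting plasma glucose.

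Section 7.1.2 makes 6.1 the rule for entry after the research nurse's assessment: "Those that are eligible (as per 6.1) will go on to complete baseline data collection". Section 7.7 then collects the funnel counts, among them "Number with possible presence of metabolic syndrome and invited to participate in study", followed by the number confirmed eligible after clinical assessment. Recruitment rate is an outcome in section 3.6, and section 10.2 makes estimating it by site a key objective.

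**The concern.** A record search that feeds an eligibility check would normally be at least as wide as the eligibility rule. Extra triggers cost some screening effort; missing triggers lose people. This list is wider than 6.1 in some places and narrower in others, and nothing in the protocol says that the narrowing is intended. The strict inequality for BMI and the restriction to statins look like drafting drift.

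At stake is the recruitment information that the feasibility study is meant to hand to the main trial (section 3.1). The first funnel count in 7.7 borrows the 7.1.1 notion of possible metabolic syndrome, while the second rests on 6.1. The ratio between them therefore reflects partly how many case-found people truly qualify and partly the disagreement between the two lists. People who arrive through a flyer or a health event need not have met the 7.1.1 list at all, so it is also unclear how they enter the first count.

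**Working it through.** The protocol states no figure that depends on either list, so there is nothing to reproduce; the precision statement in section 10.1 concerns retention. The check is a comparison of two logical rules, each true if any one item is met. Inputs are the six items in 7.1.1 and the risk criteria in 6.1. Each profile below has one risk factor present and everything else normal.

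| Only factor present | Flagged by 7.1.1 | Qualifies under 6.1 |
|---|---|---|
| Waist above the 6.1 cut-off | No | Yes |
| Total cholesterol 5.4 mmol/L | No | Yes |
| Fasting glucose 5.8 mmol/l | No | Yes |
| Lipid medication other than a statin | No | Yes |
| BMI exactly 25 (white; likewise 23 if non-white) | No | Yes |
| QRISK3 of 12% | Yes | No |
| Impaired glucose tolerance on record | Yes | No |
| Established hypertension, no medication, BP not above 130/85 | Yes | No |
| HbA1c 40 mmol/mol | Yes | Yes |
| Triglycerides 2 mmol/l | Yes | Yes |
| HDL below the cut-off | Yes | Yes |
| BMI 28 | Yes | Yes |

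Of the 12 profiles, 5 qualify without being flagged, 3 are flagged without qualifying, and 4 agree.

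Three observations follow.

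- The nurse assessment in 7.1.2 sorts out the three over-flagged profiles, because it measures waist, BMI, blood pressure, lipids and HbA1c. It does nothing for the five missed profiles on the record route, because the nurse sees only people already identified and consented.
- Fasting glucose is the sharpest case. It qualifies under 6.1 but appears neither in the 7.1.1 list, nor among the nurse's measurements in 7.1.2, nor in the Appendix A schedule.
- The BMI difference touches only people recorded exactly at 25 or 23, so it is the smallest of the five.

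How many people fall into each profile cannot be derived: the protocol gives no prevalence for any of them, alone or in combination.

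**The case against.** The best defence is that 7.1.1 is a case-finding step. It looks only for possible metabolic syndrome, and any two-stage screen loses people between finding and confirming; that loss is what the funnel is meant to show. If the main trial ran the same search, the observed conversion would carry over. The conversion is also shaped by purposive sampling (6.1), several identification routes (7.1.1) and the limits of 8 to 12 per site (7.1), so the mismatch is one influence among several. This is fair and limits the weight of the point. It explains the three extra triggers. It does not explain the five omissions, and it does not help if the main trial uses a corrected search.

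Several stronger readings are tempting but not supported.

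- A reader might infer that people with a missed profile are never invited. Section 7.1.1 also asks care teams and community project leads to inform people who meet the eligibility criteria, allows self-referral from flyers, and contacts consenting event attendees. They are missed by one route only.
- A reader might infer that people flagged on QRISK3, impaired glucose tolerance or unmedicated hypertension cannot qualify. They can, if any one 6.1 criterion is met at the nurse visit.
- A reader might infer that the trial enrols under two definitions. It does not; the risk criteria for entry are those of 6.1.
- A reader might infer avoidable blood sampling. Lipids and HbA1c are themselves 6.1 criteria, so the sample may be needed to settle eligibility, and section 7.2 has the team go through eligibility before consent.

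**Conclusion.** The two lists differ in both directions, and the protocol gives no reason for it. Followed as written, the record search passes over people whom the trial's own criteria admit, and it puts a list mismatch into the step from invited to confirmed eligible. That affects the yield of the record route and the interpretation of a recruitment outcome; it does not change the risk definition of the enrolled sample. The size is unknown and could be small: many people with SMI may carry more than one risk factor, in which case few would depend on a single mismatched item, but the protocol has no data either way. The point rests on the text of the two lists and on no numerical assumption. It merits correction because the remedy is specific and cheap.

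A separate inconsistency lies nearby. Section 7.1.2 stops people with blood pressure at stated severe levels or suspected familial hypercholesterolaemia, yet neither appears in 6.2, and the same section says that those eligible under 6.1 go on. These passages must be reconciled by the sponsor; this review takes no view on which clinical rule is right.

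**What to change.** Rewrite the 7.1.1 list so that it flags any 6.1 risk criterion that is available in the record, at the same cut-points and with the same inequality signs. If the sponsor wishes to keep triggers that are not in 6.1, such as QRISK3 or impaired glucose tolerance, say that they serve case-finding only and do not confer eligibility. Which thresholds belong in 6.1 is for the trial team.

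In 7.7, report the funnel counts by identification route and, for the record route, by the criterion that triggered the flag. Where searches have already run, this breakdown is still useful if the triggers can be retrieved, and the aligned list can carry into the main trial. Separately, reconcile the stops in 7.1.2 with the exclusions in 6.2.

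The cost is protocol wording, a small edit to the site search query, and a slightly longer list of records to review.

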# 7.1.2 Screening

# Service user participants

Following informed consent (see 7.2) obtained from identified service users as outlined above, participants will meet a research nurse in person who will go through the eligibility criteria screening (see section 6 for the Inclusion and Exclusion criteria). Demographic data including age, sex, ethnicity, will be collected. Cardio-metabolic risk data will be confirmed by a research nurse using Standard Operating Procedures to measure each indicator as defined above and as follows:

- waist circumference
- body mass index
- blood pressure
- full fasting lipid profile (including triglyceride level, high-density cholesterol, low-density cholesterol, and total cholesterol levels)
- HbA1c
- smoking status, tobacco, and betel nut or paan (or pan as it is also called) use
- alcohol consumption
- All variables collected from primary care records or by research nurse to calculate QRISK3 scores

The following data will be extracted from clinical notes, and further checked with participants:

- current mental health diagnosis
- current co-morbid physical health conditions
- current prescribed medication

Those that are eligible (as per 6.1) will go on to complete baseline data collection (See 7.6), and to be allocated to the intervention.

People identified with uncontrolled hypertension (i.e. either Systolic BP ≥200 mmHg or a diastolic BP >115 mmHg) or suspected of familial hypercholesterolaemia will be referred to their GP and will not continue in the feasibility study. People who are not eligible for the study because they do not fulfil criteria for metabolic syndrome or for other reasons will not continue in the feasibility study. They will be provided with evidence-based healthy lifestyle information by the research nurse and encouraged to make an appointment with their GP for their next annual physical health check.

# 7.1.3 Payment

Service user participants will receive a payment of £25 per data collection appointment.

#### 7.2 Consent

[figure not shown]
The Principal Investigator (PI) retains overall responsibility for the conduct of research at their site, this includes the taking of informed consent of participants at their site. They must ensure that any person delegated responsibility to participate in the informed consent process is duly authorised, trained and competent to participate according to the ethically approved protocol, principles of Good Clinical Practice (GCP) and Declaration of Helsinki. If delegation of consent is acceptable then details should be provided.

Where a potential participant contacts a member of the research team directly, or where a member of the study team contacts potential participants using their preferred contact information, they will arrange to meet them in person, by telephone or using video-conferencing application. At that meeting the member of the study team will review the Participant Information Sheet with the potential participant and answer any questions they have about the study and go through the eligibility criteria. If the potential participant is still interested in being involved, they will be invited to give informed consent. If the meeting is face-to-face, the Informed Consent Form will be signed and dated by both parties. If the meeting is by telephone or online, oral informed consent will be taken by the member of the study team who will also complete and sign the Informed Consent Form, sending a copy to the participant so that they can sign and keep a copy for their records.

Where informed consent is being provided by a service user, as part of the informed consent procedure the member of the study team will assess whether the potential participant has, at that time, capacity to give consent to be involved in research. Members of the study team will have received training in assessing capacity to consent to being involved in research.

Informed consent procedures with staff members are described in Section 7.1.1. See Figure 1 for Service User Participant Flow Diagram.

Figure I - Participant flow diagram

### 7.3 The randomisation scheme

Not relevant for this study

# 7.3.1 Method of implementing the randomisation/allocation sequence

Not relevant for this study.

# 7.4 Blinding

Not relevant for this study

# 7.5 Emergency Unblinding

Not relevant for this study.

### 7.6 Baseline data

Following eligibility screening procedures, eligible individuals will then be invited to complete the baseline data collection. Baseline data collection will be scheduled to be within a 2-week window from the eligibility screening where the blood sample forming part of the baseline trial assessment was taken.

### 7.7 Trial assessments

At baseline only, we will collect participants' sociodemographic data and QRISK3. At baseline, 3-month and 6-month time points, participants will complete further psychometric, anthropometric measures, blood tests, and self-completed assessments, as follows:

- Psychiatric symptoms using the Modified Colorado Symptom index
- · Lifestyle behaviour, measured using:
  - o Diet Dietary Instrument for Nutrition Education (DINE)(49), adapted by IMPaCT(50)
  - o International Physical Activity Questionnaire Short Form (IPAQ-SF)(51)
  - Cigarette smoking, tobacco and betel nut or paan (also spelled as pan) use smoking/paan/pan use status and number smoked per day; number of paans chewed per week
  - Alcohol Alcohol consumption test (AUDIT-C)
- Health-related quality of life measured using the EQ5D-5L
- Depression measured using the PHQ9
- Self-efficacy measured using the Generalised Self Efficacy scale
- Social network measured using the Lubben Social Network Scale
- Therapeutic relationship measured using the STAR
- Progress towards achievement of personalised lifestyle goals, measured with the Goal-based outcome tool
- DIAMONDS Service Use Survey

Service user participants will also be asked to wear a wrist-worn accelerometer for one-week periods prior to the start and in months 3 and 6 of the intervention.

The following data on recruitment, questionnaire completion and intervention attendance will be collected during the intervention period:

- Number of participants screened
- Number with possible presence of metabolic syndrome and invited to participate in study
- Number confirmed as eligible after initial clinical assessment and invited to continue to take part in intervention
- Reason for declining participation where applicable
- Intervention session attendance
- Follow-up data completion rate (questionnaires and clinical data)
- Reason for dropout where applicable

